### **7.5.5. On-Treatment ALT Flare and Post-Treatment Exacerbation of Hepatitis B Management**

An On-Treatment ALT Flare is defined as:

- Confirmed (within 3 days of receipt of initial laboratory results) serum ALT  $> 2 \times$  Day 1 value and  $> 10 \times$  ULN, with or without associated symptoms

#### **7.5.5.1. Management of ALT Flare in Subjects Receiving Study Medication**

If laboratory results indicate elevation of ALT  $> 2 \times$  Day 1 value and  $> 10 \times$  ULN, the following is recommended:

- Schedule the subject to return to the clinic as soon as possible (ideally within 3 days after initial laboratory results were drawn). During the visit, a clinical assessment of the subject will be performed. The assessment should include a physical examination and evaluation of the subject's mental status.
- If the ALT elevation is confirmed, request the central clinical laboratory to conduct reflex testing for plasma HBV DNA, HBV serology (HBsAg and HBsAb), HDV, HAV IgM, and HCV serology

Check the following laboratory parameters: serum ALT and AST, total bilirubin, INR, and serum albumin. Based on the results of the confirmatory tests, the following treatment modifications are recommended:

#### **Elevated Liver Enzymes, Normal or Stable Relative to Day 1 Liver Function Tests**

If ALT levels are elevated (i.e.,  $> 2 \times$  Day 1 and  $> 10 \times$  ULN) with normal or stable total bilirubin and INR relative to Day 1, the subject may remain on study medication and should be monitored weekly as long as ALT levels return to normal or Day 1 level. During monitoring, if the ALT values remain persistently elevated, the Investigator should discuss with the Gilead Medical Monitor whether the study drug should be discontinued.

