### **7.5.3. Grade 4 Laboratory Abnormality or Clinical Event**

- For a Grade 4 clinical event or clinically significant Grade 4 laboratory abnormality confirmed by repeat testing that is considered related to investigational medicinal product, investigational medicinal product will be permanently discontinued and the subject managed according to local practice. The subject should be followed as clinically indicated until the laboratory abnormality returns to baseline or is otherwise explained, whichever occurs first. A clinically significant Grade 4 laboratory abnormality that is not confirmed by repeat testing should be managed according to the algorithm for the new toxicity grade.
- Investigational medicinal product may be continued without dose interruption for a clinically non-significant Grade 4 laboratory abnormality (eg, Grade 4 CK lab result after strenuous exercise, or triglyceride elevation that is nonfasting or that can be medically managed) or a clinical event considered unrelated to investigational medicinal product requires discussion with the Gilead Sciences Medical Monitor.

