### **7.5.4. Management of Potential Hepatobiliary Toxicity**

Monkeys given a high dose (1000 mg/kg/day) for 39 weeks had evidence of biliary hyperplasia and hepatocyte hypertrophy on histopathologic examination. The risk to humans given the clinical dose of GS-9883 (50 mg/day) is unknown. Investigators should be aware of this potential toxicity. Any study subject exhibiting signs/symptoms or laboratory abnormalities suggestive of possible hepatobiliary toxicity should undergo thorough examination and clinical workup as deemed appropriate by the Investigator, and the Investigator must communicate promptly with the Gilead Medical Monitor. Consideration should be given to appropriate imaging studies (for example, ultrasound of the liver and biliary tree) and potential consultation with a gastroenterologist with specialty training in hepatobiliary diseases. Management of graded laboratory and clinical abnormalities will be managed as outlined in Section 7.5.

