#### **Elevated Liver Enzymes, Elevated Liver Function Tests**

If ALT values are elevated (i.e.,  $> 2 \times$  Day 1 and  $> 10 \times$  ULN), and total bilirubin is confirmed to be  $2 \times$  Day 1 value, and INR is 0.5 above Day 1, provided both are  $>$  ULN, the investigator should consider discontinuing study medication (upon discussion with the Gilead Medical Monitor, unless the safety of the patient is of immediate concern). The subject should be monitored weekly as long as ALT, total bilirubin, and INR values remain elevated or above Day 1 values.

During monitoring, if the ALT values and the liver function tests remain persistently elevated, the Investigator should discuss with the Gilead Medical Monitor whether the study drug should be discontinued.

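### A confirmed ALT flare judged drug related and clinically significant falls under both a mandatory stop (Section 7.5.3) and permission to continue (Section 7.5.5.1), with no precedence stated in the available text

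*Protocol*

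**What the plan says.** Protocol Section 7.5 has general rules by toxicity grade (7.5.1 to 7.5.3), followed by rules for named situations (7.5.4 to 7.5.8).

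- **Section 7.5.3 (Grade 4).** The mandatory stop covers a Grade 4 clinical event or a clinically significant Grade 4 laboratory value "confirmed by repeat testing that is considered related to investigational medicinal product, investigational medicinal product will be permanently discontinued". The same section has an exception: "Investigational medicinal product may be continued without dose interruption for a clinically non-significant Grade 4 laboratory abnormality".
- **Appendix 4.** ALT above 10.00 × ULN is Grade 4.
- **Section 7.5.5.** An on-treatment ALT flare is a confirmed ALT above both 2 × Day 1 and 10 × ULN. Neither causality nor hepatitis B status is part of the definition.
- **Section 7.5.5.1, bilirubin and INR normal or stable.** "the subject may remain on study medication and should be monitored weekly as long as ALT levels return to normal or Day 1 level".
- **Section 7.5.5.1, bilirubin and INR both raised.** "the investigator should consider discontinuing study medication", after discussion with the Medical Monitor unless there is an immediate safety concern. On monitoring: "The subject should be monitored weekly as long as ALT, total bilirubin, and INR values remain elevated or above Day 1 values".
- **Section 7.5.4 (hepatobiliary toxicity).** "Management of graded laboratory and clinical abnormalities will be managed as outlined in Section 7.5".

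**The concern.** One laboratory result leads to two instructions. A site that works from the Grade 4 rule stops the drug for good. A site that works from the flare rule may keep the woman on it. Both have followed the protocol.

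The neighbouring Grade 3 rule makes the mismatch plainer. Section 7.5.2 has study drug withheld for a confirmed, related, clinically significant Grade 3 value, which for ALT means above 5.00 and up to 10.00 × ULN. Set beside Section 7.5.5.1, a lower related ALT calls for an interruption while a higher one may continue without one.

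This matters because Section 1.11 names hepatobiliary toxicity as a potential risk and relies on specific toxicity guidance to manage it. Section 7.5 is that guidance. Inconsistent handling would also blur the summaries of discontinuations due to adverse events.

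The weekly-monitoring condition in the first limb of Section 7.5.5.1 adds to the difficulty: it is tied to ALT returning to normal, whereas its companion sentence is tied to values staying high.

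**Working it through.** No sample size, power or alpha figure is involved, so there is no stated figure to reproduce. The check compares thresholds and texts.

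**1. Is every flare Grade 4?** The flare cut-off is above 10 × ULN (Section 7.5.5) and the ALT Grade 4 cut-off is above 10.00 × ULN (Appendix 4). They are identical, so every flare is Grade 4.

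**2. Does confirmation separate the rules?** No. Section 7.5 has Grade 3 and 4 values repeated within 3 calendar days of receiving results, and Section 7.5.5 confirms a flare within 3 days of receipt. A confirmed flare is a confirmed Grade 4 value.

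**3. Does the 2 × Day 1 condition separate them?** Inclusion criterion 9 caps ALT at 5 × ULN. If Day 1 ALT is still within that cap, 2 × Day 1 is at most 2 × 5 = 10 × ULN, and any ALT above 10 × ULN also exceeds 2 × Day 1. The rules part only if Day 1 ALT has risen above the cap. At a Day 1 value of 6 × ULN, for example, the flare threshold is 2 × 6 = 12 × ULN, and a value of 11 × ULN is Grade 4 but not a flare.

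**4. Actions side by side for a confirmed ALT flare.**

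| Investigator's judgement | Section 7.5.3 | Section 7.5.5.1 | Conflict? |
|---|---|---|---|
| Related, clinically significant; bilirubin and INR normal or stable | Permanent stop | May stay on drug | Yes |
| Related, clinically significant; bilirubin and INR both raised | Permanent stop | Stopping to be considered | Yes |
| Clinically non-significant | May continue | As above | No |
| Unrelated | Mandatory stop does not apply | As above | No |

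**5. Is there a tie-break?** The opening of Section 7.5 places all clinical and clinically significant laboratory toxicities under one uniform set of guidelines and makes no exception for flares. Section 7.5.4 sends graded abnormalities back to Section 7.5 as a whole. Sections 7.5.5 and 7.5.5.1 do not say that they override 7.5.3. The heading of 7.5.5 mentions hepatitis B, but the flare definition and the on-treatment management text carry no such limit, and viral testing is requested only once the rise is confirmed. Section 7.5 also points to Appendix 3, whose chart is not shown in the available text.

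**6. Monitoring wording.** Three sentences can be compared:
- Section 7.5.5.1, first limb: weekly as long as ALT returns to normal or to Day 1.
- Section 7.5.5.1, second limb: weekly while ALT, bilirubin and INR are still high.
- Section 7.5.5.2, after stopping: follow-up until the values are back to normal or Day 1, for at most 6 months.

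Read literally, the first attaches monitoring to recovery and the other two attach it to the abnormality.

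**7. Route to the endpoint.** Under the snapshot rules (Section 8.5.1.1), a stop for a reason other than lack of efficacy, with last on-treatment RNA below 50, gives no virologic data only if there is no on-treatment RNA in Days 295 to 378. With an on-treatment value below 50 in that window, the woman counts as below 50. The no-data category is not a failure in the primary endpoint, which counts RNA of 50 or more. It can lower the secondary proportion below 50, and it removes the woman from the Week 48 per-protocol set (Section 8.2.1.2.2).

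**The case against.** The best defence is that the specific rule governs the general one. Sections 7.5.4 to 7.5.8 deal with named situations, and Section 7.5.6 appears to work that way: bilirubin above 5.0 × ULN is Grade 4 in Appendix 4, yet isolated values of 5 to 10 × ULN may continue. This reading is plausible, but the available text never states it. The bilirubin example can also be squared with the clinically non-significant exception in 7.5.3, because the protocol describes those atazanavir rises as mostly asymptomatic. A flare that the investigator has judged clinically significant cannot be squared that way.

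A second defence is that the Medical Monitor will sort it out. Section 7.5.4 requires prompt contact for suspected hepatobiliary toxicity, and Section 7.5.5.1 brings the Monitor in for persistent rises. This lowers the practical risk and stands as mitigation, but it does not tell the site or the Monitor which section applies.

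Three stronger readings are tempting and are not supported:

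- *Any confirmed, drug-related ALT above 10 × ULN must be stopped under 7.5.3.* The laboratory limb is limited to a "clinically significant Grade 4 laboratory abnormality confirmed by repeat testing", and relatedness is a further condition. Permission to remain on drug in 7.5.5.1 is itself limited to normal or stable bilirubin and INR.
- *The monitoring sentence tells sites to stop watching a raised ALT.* The sentence that follows it covers ALT that stays raised during monitoring, so monitoring of a raised ALT is presupposed. The condition could also be meant to qualify staying on drug. The phrase is ambiguous, and its intent can be recovered from context.
- *The conflict biases the primary analysis.* Step 7 of the working does not show this.

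**Conclusion.** The inconsistency is real but narrow. It covers every confirmed flare that the investigator judges both drug related and clinically significant, whether or not bilirubin and INR are raised. Outside that group the two sections can be followed together.

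The documents give no flare frequency, so the number of women affected cannot be stated. No effect on the primary endpoint, sample size, power or alpha is shown.

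The identity of the two ALT thresholds needs no assumption. The finding that the Day 1 condition fails to separate the rules assumes Day 1 ALT within the entry limit of 5 × ULN. The finding on precedence rests on the available text only: a tie-break in the Appendix 3 chart cannot be excluded. The monitoring phrase is a lesser drafting fault. The point still merits correction, because an operative safety rule gives conflicting instructions as written.

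**What to change.** Amend the wording of Sections 7.5.3 and 7.5.5.1:

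1. State which section governs a confirmed, drug-related, clinically significant ALT above 10 × ULN, for both limbs of 7.5.5.1.
2. State in which subjects 7.5.5.1 applies: all subjects, or only those with hepatitis B.
3. Reconcile the weekly-monitoring condition in the first limb of 7.5.5.1 with the second limb and with Section 7.5.5.2.
4. Check that the Appendix 3 chart agrees with the reconciled text.

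The choice of clinical rule belongs to the sponsor's medical team, and no view is taken here. The cost is a wording amendment with the usual ethics committee submission (Section 9.2.1). It adds no new procedure and does not change the statistical design.

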#### **Elevated Liver Enzymes, Elevated Liver Function Tests**

If ALT values are elevated (i.e.,  $> 2 \times$  Day 1 and  $> 10 \times$  ULN), and total bilirubin is confirmed to be  $2 \times$  Day 1 value, and INR is 0.5 above Day 1, provided both are  $>$  ULN, the investigator should consider discontinuing study medication (upon discussion with the Gilead Medical Monitor, unless the safety of the patient is of immediate concern). The subject should be monitored weekly as long as ALT, total bilirubin, and INR values remain elevated or above Day 1 values.

During monitoring, if the ALT values and the liver function tests remain persistently elevated, the Investigator should discuss with the Gilead Medical Monitor whether the study drug should be discontinued.

#### 7.5.5.2. Management of Exacerbation of Hepatitis B in Subjects Who Have Discontinued Study Medication

If laboratory results indicate (1) an ALT elevation  $> 2 \times$  Day 1 and  $> 10 \times$  ULN alone OR associated with (2) abnormal laboratory parameters suggestive of worsening hepatic function (total bilirubin  $2 \times$  Day 1, INR 0.5 above Day 1, provided both are  $>$  ULN) and the subject is on no post-study therapy for HBV, the following is recommended:

- Schedule the subject to return to the clinic as soon as possible (ideally no later than 3 days after the initial laboratory values were drawn). During the visit, perform a clinical assessment of the subject.
- Check the following laboratory parameters: serum ALT and AST, bilirubin, INR, and albumin.
- If the ALT elevation is confirmed, request the clinical laboratory to conduct reflex testing for plasma HBV DNA, HBV serology (HBsAg and HBsAb), HDV, HAV IgM and HCV. If serum HBV DNA is increasing, the investigator should consider immediate initiation of approved therapy.
- The subject should be followed until laboratory parameters (ALT, total bilirubin, INR) return to normal or Day 1 up to a maximum of 6 months after the initial occurrence of the event.

#### 7.5.6. Management of Hyperbilirubinemia

Most patients taking atazanavir sulfate experience asymptomatic elevations in indirect (unconjugated) bilirubin related to inhibition of UDP-glucuronyl transferase (UGT). Hepatic transaminase elevations that occur with hyperbilirubinemia should be evaluated for alternative etiologies. Dose modification of atazanavir sulfate is not permitted. Subjects who experience unacceptable jaundice/scleral icterus can be discontinued from study at the discretion of the Investigator.

- Subjects with bilirubin levels of  $5-10 \times$  ULN, if isolated and not accompanied by unacceptable clinical jaundice (scleral icterus or cutaneous jaundice) may continue on study, if agreed upon by the subject and the Investigator. All subjects with serum bilirubin levels  $5-10 \times$  ULN must have bilirubin, AST and ALT repeated at least once within 7 days of the Investigator being notified of the elevated bilirubin level. Thereafter, serum bilirubin levels  $5-10 \times$  ULN without clinically significant elevation in AST or ALT should be followed according to the clinical judgment of the Investigator.
- Subjects whose hyperbilirubinemia ( $5-10 \times$  ULN) is accompanied by  $\geq$  Grade 2 ALT or AST elevation or who experience a one Grade worsening in ALT or AST do not qualify as having isolated hyperbilirubinemia and will be discontinued.
- Confirmed hyperbilirubinemia  $> 10 \times$  ULN will require discontinuation.
- Elevation of conjugated (direct) bilirubin  $> 2$  mg/dL in association with Grade 2 ALT or AST elevation will require discontinuation.

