#### **1.2.2.1. Pharmacology**

GS-9883 has half maximal inhibitory concentration ( $IC_{50}$ ) values ranging from 1.5 to 2.4 nM, similar to the inhibitory effect of DTG and EVG. GS-9883 is highly potent against HIV replication in the human T cell leukemia MT4 cell line with an  $EC_{50}$  (50% effective inhibitory concentration) value of 1.9 nM and a protein adjusted  $EC_{95}$  value of 361 nM. GS-9883 does not show significant cytotoxicity against dividing and non-dividing human PBMCs, primary human hepatocytes and various non-target human cell lines.

GS-9883 is mainly metabolized by uridine 5'-diphospho-glucuronosyltransferase (UGT1A1) and CYP3A. GS-9883 does not inhibit major human CYP isoforms or UGT1A1 at concentrations up to 25  $\mu$ M. Consequently, GS-9883 is unlikely to be a clinically relevant inhibitor of these enzymes, and is not expected to inhibit the metabolic clearance of drugs metabolized by these enzymes. GS-9883 only modestly inhibits renal transporter organic cation transporter 2 (OCT2) ( $IC_{50}$  = 0.42  $\mu$ M). As a result, GS-9883 is not expected to significantly interfere with the key

transporter responsible for creatinine tubular elimination at the clinically projected  $C_{max}$ . Additionally, the risk that GS-9883 will affect the OCT2-mediated excretion of co-administered drugs is considered to be low.

GS-9883 does not activate AhR and only weakly activates PXR at concentrations up to 50  $\mu$ M (less than 5% and 40% of activation, respectively, compared to positive control compound). Therefore, GS-9883 is not expected to act as an inducer through PXR- or AhR-mediated pathways at the doses and exposure levels projected in clinical use.

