In a 39-week study in monkeys (TX-141-2032), following administration of 1000 mg/kg/day (high dose) of GS-9883 for 39 weeks, pathology data indicated minimal to marked bile duct hyperplasia and minimal or moderate hepatocyte hypertrophy in both sexes, and minimal regenerative hyperplasia and minimal or slight neutrophil infiltrate in males. The macroscopic finding of rough surface on the liver in one male administered 1000 mg/kg/day correlated with moderate hepatocyte hypertrophy and marked bile duct hyperplasia. After a 4-week recovery period, GS-9883-related microscopic liver findings included marked bile duct hyperplasia, slight hepatocyte hypertrophy, minimal regenerative hyperplasia, and slight lymphocyte infiltrate in one male and slight bile duct hyperplasia in one female administered 1000 mg/kg/day, while the other two animals in the high dose group had no hepatobiliary findings. Minimally to mildly increased ALT activities ( $\leq$  3.5-fold versus baseline values), likely associated with liver findings, exhibited reversibility. There were no other adverse findings in the study, including clinical observations, or effects on body weight, body weight change, food consumption, ECGs, hematology, coagulation, clinical chemistry, urinalysis, and ophthalmoscopy.

No GS-9883-related effects were observed in the mid-dose group (200 mg/kg/day) which was considered the no-observed-effect-level (NOEL). The estimated margin of exposure at the NOEL was approximately 5.1-fold based on expected human exposure with the once daily dosing of the GS-9883/F/TAF (50/200/25 mg) tablet.

A standard battery of in vitro and in vivo studies was performed to assess the genotoxic potential of GS-9883. There was no evidence of mutagenic or clastogenic activity in an in vitro bacterial reverse mutation assay (Study TX-141-2026), a chromosomal aberration assay in human lymphocytes (Study TX-141-2027), or in a rat micronucleus test (Study TX-141-2029).

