### 4.2. Inclusion Criteria

Subjects must meet **all** of the following inclusion criteria to be eligible for participation in this study.

- 1) The ability to understand and sign a written informed consent form, which must be obtained prior to initiation of study procedures
- 2) Female, (at birth), Age  $\geq$  18 years
- 3) Currently on a stable antiretroviral regimen of E/C/F/TAF, E/C/F/TDF, or ATV+RTV+FTC/TDF continuously for  $\geq$  12 consecutive weeks preceding the screening visit
- 4) Completion of the Week 48 OLE visit or any post Week 48 OLE visits in study GS-US-236-0128, completion of the Week 96 visit or any post Week 96 visits in study GS-US-292-0109, or completion of the Week 144 visit or any post Week 144 visits in studies GS-US-292-0104 or GS-US-292-0111
- 5) Documented plasma HIV-1 RNA levels  $<$  50 copies/mL for  $\geq$  12 weeks preceding the Screening Visit. After reaching HIV-1 RNA  $<$  50 copies/mL, single values of HIV-1 RNA  $\geq$  50 copies/mL followed by resuppression to  $<$  50 copies/mL are allowed
- 6) HIV-1 RNA  $<$  50 copies/mL at screening
- 7) Normal ECG (or if abnormal, determined by the Investigator to be not clinically significant)
- 8) Adequate renal function:  
Estimated glomerular filtration rate  $\geq$  50 mL/min ( $\geq$  0.83 mL/sec) according to the Cockcroft-Gault formula [{Cockcroft et al 1976}](#):

$$\frac{(140 - \text{age in years}) \times (\text{wt in kg})}{72 \times (\text{serum creatinine in mg/dL})} \times 0.85 = \text{CrCL (mL/min)}$$

$$\frac{(140 - \text{age in years}) \times (\text{wt in kg}) \times 0.85}{72 \times (\text{serum creatinine in } \mu\text{mol/L}) \times 0.6786} = \text{CrCL (mL/sec)}$$

- 9) Hepatic transaminases (AST and ALT)  $\leq 5 \times$  upper limit of normal (ULN).
- 10) Total bilirubin  $\leq 1.5$  mg/dL ( $\leq 26 \mu\text{mol/L}$ ), or normal direct bilirubin.

- 11) Adequate hematologic function (absolute neutrophil count  $\geq 750/\text{mm}^3$  ( $\geq 0.75 \text{ GI/L}$ ); platelets  $\geq 50,000/\text{mm}^3$  ( $\geq 50 \text{ GI/L}$ ); hemoglobin  $\geq 8.5 \text{ g/dL}$  ( $\geq 85 \text{ g/L}$ )).
- 12) Serum amylase  $\leq 5 \times \text{ULN}$  (subjects with serum amylase  $> 5 \times \text{ULN}$  will remain eligible if serum lipase is  $\leq 5 \times \text{ULN}$ ).

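### Section 7.5.6 opens an atazanavir-based bilirubin allowance to every regimen, and the protocol does not say whether it or 7.5.3 governs Grade 4 bilirubin in women not taking atazanavir

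*Protocol*

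**What the plan says.** Protocol section 7.5.6 opens with its rationale: "Most patients taking atazanavir sulfate experience asymptomatic elevations in indirect (unconjugated) bilirubin related to inhibition of UDP-glucuronyl transferase (UGT"). Four bullets follow, none limited to a regimen.

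- **First bullet.** At 5-10 x ULN, a subject whose rise is isolated and without unacceptable clinical jaundice "scleral icterus or cutaneous jaundice) may continue on study, if agreed upon by the subject and the Investigator". Bilirubin, AST and ALT must be "repeated at least once within 7 days of the Investigator being notified of the elevated bilirubin level". The Medical Monitor is not mentioned.
- **Second bullet.** Subjects in the same band with Grade 2 or higher ALT or AST, or a one-grade worsening, "do not qualify as having isolated hyperbilirubinemia and will be discontinued".
- **Third bullet.** Confirmed bilirubin above 10 x ULN requires discontinuation.
- **Fourth bullet.** Direct bilirubin above 2 mg/dL "in association with Grade 2 ALT or AST elevation will require discontinuation".

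Elsewhere in the Protocol:

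- Appendix 4 grades adult bilirubin above 5 x ULN as Grade 4.
- Section 7.5 asks for clinically significant Grade 3-4 results to be repeated within 3 calendar days.
- Section 7.5.3 permanently stops drug for a confirmed, clinically significant Grade 4 laboratory value judged related. It lets drug continue when the value is not clinically significant.
- Section 7.5.4 requires work-up and prompt Medical Monitor contact for any subject with findings that suggest hepatobiliary toxicity.
- Inclusion criterion 10 uses the bilirubin fraction: total bilirubin up to 1.5 mg/dL, "or normal direct bilirubin".
- Section 1.2.2.1 states that "GS-9883 does not inhibit major human CYP isoforms or UGT1A1 at concentrations up to 25" µM.
- Section 1.2.2.2 reports "minimal to marked bile duct hyperplasia and minimal or moderate hepatocyte hypertrophy in both sexes" in monkeys at the high dose.

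**The concern.** The allowance makes sense for ATV, where an isolated indirect rise is a known and benign drug effect. As written, it also covers women on GS-9883/F/TAF, E/C/F/TAF and E/C/F/TDF, and the protocol gives no such explanation for a bilirubin of that size on those regimens. For GS-9883 the mechanism offered is contradicted by section 1.2.2.1, and 7.5.4 calls the human relevance of the monkey biliary finding unknown.

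Two things follow. First, for a woman not on ATV, 7.5.6 permits what 7.5.3 can forbid. An investigator could take 7.5.6 as governing because it is the rule specific to bilirubin. Second, the measurement that separates an ATV-type rise from a cholestatic one is the direct fraction, and the allowance makes no use of it. At stake is consistent handling of a rare but serious laboratory result, not any efficacy conclusion.

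**Working it through.** The plan gives no figure on this point to reproduce. The check sets the rules side by side and then sizes the affected groups.

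**1. Outcomes under 7.5.6 alone, bilirubin 5-10 x ULN**

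| ALT/AST | Direct > 2 mg/dL | Unacceptable jaundice | Result under 7.5.6 |
|---|---|---|---|
| Grade 0-1, no grade worsening | No | No | May continue by agreement |
| Grade 0-1, no grade worsening | Yes | No | May continue by agreement |
| Grade 0-1, no grade worsening | Either | Yes | Allowance not available; Investigator may discontinue |
| Grade 2 or higher, or one grade worse | Either | Either | Discontinued by the second bullet |

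The first two rows differ only in direct bilirubin and have the same result. The fourth bullet adds nothing in this band, because every case with Grade 2 ALT or AST is already stopped by the second. It can matter only below 5 x ULN.

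**2. 7.5.6 against 7.5.3**

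Take a woman on GS-9883/F/TAF with a confirmed value of 7 x ULN, ALT and AST unchanged and no jaundice.

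| Judgement on the value | 7.5.3 | 7.5.6, first bullet |
|---|---|---|
| Related and clinically significant | Permanent stop | May continue by agreement |
| Unrelated, or not clinically significant | No stop ordered | May continue by agreement |

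The rules disagree in the first row only. Section 7.5.4 does not settle it: its last sentence refers graded abnormalities back to section 7.5, which contains both rules.

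**3. Whom the rationale fits**

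- GS-9883/F/TAF to Week 48: 235/470 = 50%. After Week 48 it is the only drug dispensed (Protocol Appendix 2, footnote v). The ATV rationale fits none of these women.
- ATV: the share of the SBR arm is not given. Assuming 10-30%, 0.10 x 235 = 23.5 and 0.30 x 235 = 70.5 women, which is 23.5/470 = 5% to 70.5/470 = 15% of the trial.

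**4. Whether a fixed direct-bilirubin cut-off would do**

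The fourth bullet's 2 mg/dL is the obvious candidate. The ULN is not given; assume 0.8-1.3 mg/dL.

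- At 5 x ULN (4.0-6.5 mg/dL), 2 mg/dL is 2/4.0 = 50% to 2/6.5 = 31% of the total.
- At 10 x ULN (8-13 mg/dL), it is 2/8 = 25% to 2/13 = 15%.

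Near the top of the band the cut-off would therefore catch ATV women whose rise is still mainly indirect. A criterion based on which fraction predominates avoids this.

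**5. Retest timing**

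The difference is 7 - 3 = 4 days. Seven days is an outer limit, and a retest by day 3 satisfies both rules.

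**The case against.** The strongest reply is that other rules already cover these women. Section 7.5.4 applies to any subject and obliges the Investigator to contact the Medical Monitor promptly. Section 6.7 lets the Investigator stop drug for toxicity. ALP and GGT have their own Grade 3 and 4 thresholds under 7.5.2 and 7.5.3. When the value is judged unrelated or not clinically significant, limiting the bullet would not change the drug decision. All of this stands, and it is why the point is minor. It does not resolve the related, clinically significant case.

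A second reply is that the bullet only permits while 7.5.3 commands, so 7.5.3 should win. Continuing on study might also mean staying in follow-up rather than on drug. Both readings are possible, but the protocol states neither, and a specific rule is often taken to displace a general one.

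A third is that isolated is never fully defined: the second bullet names cases that fail without saying they are the only ones, and the opening sentence frames the rise as indirect. That is fair, and it supports writing the condition down. Nor does an entry criterion have to be mirrored on treatment; criterion 10 shows only that the fraction was thought informative.

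A reader might infer more than the documents support:

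- That anyone at 5-10 x ULN may stay on drug. The bullet requires an isolated rise without unacceptable jaundice.
- That the 3-day and 7-day retests contradict each other. Both can be met.
- That a mainly direct rise is to be expected on GS-9883. The monkey laboratory correlate was ALT, which 7.5.6 does test, and section 1.11 says no liver or bile duct drug reaction had been identified in humans.

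**Conclusion.** The point holds in a limited form. The first bullet of 7.5.6 applies an ATV-specific allowance to all regimens. For women not on ATV it conflicts with 7.5.3 when a Grade 4 bilirubin is confirmed, related and clinically significant, and no precedence is given. In the 5-10 x ULN band direct bilirubin has no effect on any 7.5.6 outcome.

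Severity is minor. The 50% is an arm share, not a frequency of the problem; with no event rate in the documents, the number of women affected cannot be computed. The ATV share and the ULN above are assumptions. The body of Appendix 3, to which 7.5 refers for uniform guidelines, was not available for this check and might settle precedence. The primary endpoint, sample size and analysis are not affected.

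**What to change.** Amend the first bullet of 7.5.6 only.

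1. Limit the allowance to subjects taking ATV whose rise is isolated and predominantly indirect (for example, direct bilirubin less than half of total), with no unacceptable jaundice. Say that it concerns continuing study drug and that for these subjects it takes precedence over 7.5.3. Keep the 7-day retest for them.
2. State that subjects not taking ATV are managed under 7.5.2-7.5.4, with total and direct bilirubin, AST and ALT repeated within 3 calendar days and prompt Medical Monitor contact.
3. For ATV subjects with a predominantly direct rise, require the 7.5.4 work-up and a Medical Monitor discussion. Do not use a fixed 2 mg/dL cut-off that sends them to 7.5.3: their rise is likely to be called related, and a known ATV effect could then lead to a permanent stop.
4. Leave the three discontinuation bullets as they are, for all subjects.

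The cost is a wording change, a note to sites, and a few earlier retests and Medical Monitor contacts. Direct and indirect bilirubin are already in the chemistry profile, so no new test or scheduled visit is needed.
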